### **4.4 Early Withdrawal of Subjects**

Subjects will be considered to have completed the study after completion of the last study visit (follow-up phone call). Subjects may be withdrawn prior to this for any of the following reasons:

- Death, or
- Lost to Follow-Up, or
- Withdrawal of consent, or
- Discontinuation by the investigator.

Documentation must be maintained at the site for any subject withdrawals. Subjects unable to complete Cytosponge administration will be withdrawn from the study (discontinued by investigator). Three attempts at contact using two different methods are required prior to determination that the subject is lost to follow-up. Attempts at contact must be with certified letters OR documented telephone contact. If a subject is withdrawn prior to completion of the study, the site should complete and submit a change of status case report form. See section 8.3 for additional information on case report forms. Subjects who withdraw after completion of the initial Cytosponge administration will not be replaced. Withdrawn subjects will not be followed, unless they have an active adverse event (AE) at the time of withdrawal. Subjects withdrawn while experiencing an adverse event will be followed until resolution of the AE.

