Subject recruitment will be from consecutive eligible patients presenting for routine care surveillance endoscopy of current BE or following endoscopic ablation of BE. Potentially eligible subjects will be contacted by telephone in advance of their procedure and their interest in study participation assessed. Subjects interested in participating will be asked to present to the endoscopy unit one hour prior to their scheduled procedure. At that time, inclusion and exclusion criteria will be reviewed, and eligible subjects will give informed consent. Subjects will then undergo the Cytosponge assay. Following Cytosponge assay, subjects will complete the procedure acceptability measures described below. Subjects will then attend their usual surveillance endoscopy session. Upper endoscopy will be performed and biopsies taken as part of routine care. Importantly, no record of the results of the standard endoscopy and biopsies will be provided to those assessing the Cytosponge results and these individuals will be masked to all clinical data. Similarly, the pathologists interpreting the histological specimens from the endoscopy will have no knowledge of the outcomes of the Cytosponge assay. Only the study biostatistician will have access to these data.

Primary assessment of acceptability will be via the Impact of Events Scale. This widely used scale was developed to assess the distress associated with a specific life event. It includes measures of both the intrusiveness of the event, and any avoidance responses by the subject in response to the event. Final scores are between 0-75, with low scores demonstrating a low impact of the event. The scale will be administered 7 days after the sampling in order to allow the subjects to have time to reflect on the experience and to compare with the EGD. Secondary acceptability outcomes will include a visual analogue scale of acceptability of the Cytosponge, performed after the Cytosponge is administered. Also, the subject will be asked whether he/she would be willing to repeat the assay, and, assuming similar accuracy between Cytosponge and upper endoscopy, whether he/she would rather undergo surveillance by Cytosponge or standard EGD with biopsies.

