## 5 Study Procedures

Assessment	Screening/Enrollment Visit	Follow-Up Phone Call (7 days +/- 2 days after Enrollment)	Repeat Cytosponge (30 days +/- 10 days after Enrollment)
Informed Consent Form	X		
Demographics	X		
Medical History	X		
Inclusion/Exclusion Criteria	X		
Cytosponge Administration	X		X 
Visual Analogue Scale	X 		
Routine Care Endoscopy with Biopsy	X 		
Impact of Events Scale		X	
Procedure Preference and Acceptability Questionnaire		X	
Adverse Events	X	X	X

If the initial Cytosponge sample is inadequate, sites will be notified and subjects will be asked to return for repeat Cytosponge administration 30 days (+/- 10 days) after the initial Cytosponge administration. Only the Cytosponge administration will be repeated. Questionnaires and the endoscopy procedure will not be repeated on these patients.

VAS should be administered immediately following completion of the Cytosponge and prior to the upper endoscopy.

Routine care biopsies should be taken during the endoscopy following the Cytosponge as this is considered standard of care for the target population. No research-specific biopsies will be obtained during the procedure.

Only those events that are potentially related to participation in this research study must be reported. See section 7.2 for definition of a reportable adverse event.

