### **5.1.3 Cytosponge Administration**

The Cytosponge™ device (referred to hereafter as the "Cytosponge") will be supplied by Covidien GI Solutions to the participating sites. Study sites will be responsible for storage and accountability of the device. The Cytosponge lifetime/use by date will be confirmed on the product packaging. The device received FDA 510(k) clearance on November 26, 2014 (K142695). The Cytosponge device consists of a spherical 3.0 cm diameter reticulated polyester foam compressed and encapsulated in a standard vegetarian capsule (size 00).

Subjects will undergo administration of the Cytosponge™ according to the IFU. Briefly, subjects will be placed in the seated position and will swallow the capsule with 150 – 250 mL of water. Additional water may be used if necessary. The sponge is attached to a length of suture material which passes out through the capsule. The suture is affixed to a retainer card which is held by the subject or administrator to prevent inadvertent swallowing of the suture. The string is to be held without tension as peristalsis and gravity advance the capsule into the stomach.

The capsule dissolves in the stomach, allowing the sponge to expand to its full size. Seven minutes and 30 seconds to ten minutes after ingestion, the sponge is then withdrawn by gentle traction on the suture, collecting cells from the lining of the esophagus in passing.

After retrieval, the string is cut and the retrieved foam sphere containing the cytological specimen is immersed in fixative and stored refrigerated (1° to 12°C [34° to 54°F]) until shipped. Samples will be shipped in batches to the [name] Lab in Cambridge. On arrival at the [name] lab, the fixative is spun in a centrifuge, and the pelleted cells are embedded in paraffin using standard techniques. The blocks are sectioned and stained for trefoil factor 3, where any staining is considered positive for the assay.

If a subject fails to swallow the Cytosponge, the subject will be asked to swallow again. Subjects who are willing to try again will be asked to wait 5 minutes before the Cytosponge is presented to them again. Subjects will be able to try up to three times before they are classified as "Cytosponge swallowing failure" and discontinued by the investigator.

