### **5.2.3 Procedure Preference and Acceptability Questionnaire**

The procedure preference and acceptability questionnaire will be completed with the subject during the follow-up phone call. This assessment collects subject preference for the Cytosponge or traditional upper endoscopy as well as willingness to undergo the procedure again.

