## 6.3 Subject Population for Analysis

The population whose data will be subjected to the study analysis will include all subjects enrolled in this study that completed the Cytosponge administration and have pathology results available from the subsequent routine care endoscopy with biopsy.

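### Acceptability is measured and analysed only in subjects who complete the Cytosponge; those who attempt it and fail are withdrawn, and no failure proportion is planned

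*Combined protocol and SAP*

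**What the plan says.** The rule is spread over several sections of the combined protocol and SAP.

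- **Swallowing failure (5.1.3).** "Subjects will be able to try up to three times before they are classified as" a swallowing failure and discontinued by the investigator.
- **Withdrawal (4.4).** "Subjects unable to complete Cytosponge administration will be withdrawn from the study (discontinued by investigator". The same section adds: "Withdrawn subjects will not be followed, unless they have an active adverse event (AE) at the time of withdrawal".
- **VAS (section 5 table, note 2).** "VAS should be administered immediately following completion of the Cytosponge and prior to the upper endoscopy".
- **IES (3.1).** "The scale will be administered 7 days after the sampling"; sections 5.2.1 and 5.2.2 place it in the follow-up call.
- **Preference and willingness to repeat (5.2.3).** "The procedure preference and acceptability questionnaire will be completed with the subject during the follow-up phone call".
- **Analysis population (6.3).** Only one is defined: "all subjects enrolled in this study that completed the Cytosponge administration" and who also have pathology results from the endoscopy.
- **Replacement (4.4).** "Subjects who withdraw after completion of the initial Cytosponge administration will not be replaced". Nothing is said about subjects who never complete.

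Section 2 makes acceptability in subjects under surveillance after RFA the primary objective, and section 6.2 analyses it as such. Sections 3.1, 3.3 and 3.4 instead rank it among the secondary outcomes, behind sensitivity and specificity. Neither ranking limits it to completers. Section 6.2 lists IES, VAS, preference and willingness, but no swallowing-failure or completion proportion.

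**The concern.** Being unable to get the capsule down is itself evidence about acceptability. Under these rules such a subject contributes no VAS, no IES, no preference and no willingness answer, and is outside the analysis set in any case. The subject leaves the denominator as well as the numerator.

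Section 1.1 puts forward the central hypothesis that the device could supplant endoscopy in this population. For that purpose the relevant denominator is everyone asked to swallow it. The protocol uses that denominator for its own background evidence: section 1.3.1 supports good tolerance by reporting how many of 504 patients could swallow the capsule. As planned, this trial's analysis would not yield the matching figure.

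Section 6.2 also plans a logistic model for predictors of low tolerance. If low tolerance is rare, as the hypothesis expects, even a few missing failures could be a noticeable share of the informative cases.

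**Working it through.** **Step 1: is there any route by which a failure is measured?** Setting the rules side by side:

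- VAS: tied to completion. A score after a failed attempt is not expressly forbidden, but section 6.3 would leave it out of the analysis.
- IES, preference, willingness: day-7 call only. A withdrawn subject is not followed unless an adverse event is active, and that exception concerns the event, not the questionnaires.
- Failure count: section 4.4 requires each withdrawal to be documented on a change of status form (also listed in 8.3.1), so the count will exist. No analysis in 6.2 uses it.

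No other section repairs this.

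**Step 2: the documented failure rate.** Section 1.3.1 gives 501 of 504 successful swallows, stated as 99%.

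- 501/504 = 99.4%, consistent with the stated figure.
- Failures: 3/504 = 0.60%; exact (Clopper-Pearson) 95% CI 0.12% to 1.73%.
- Expected among the 324 post-ablation subjects of section 6.1: 324 × 3/504 = 1.9, about 2. At the upper limit: 324 × 0.0173 = 5.6, about 6.

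**Step 3: effect on a proportion.** Let q be the proportion willing among completers and f the failure proportion. If every failure is unwilling, the proportion among all who attempted is q × (1 − f), and the completer figure is too high by q × f. The documents give no expected q; 85% is an illustration.

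| f | Source | Failures of 324 | q × (1 − f) | Overstatement (points) |
|---|---|---|---|---|
| 0.60% | 3/504 | 1.9 | 84.5% | 0.5 |
| 1.73% | upper 95% limit | 5.6 | 83.5% | 1.5 |
| 2% | assumption | 6.5 | 83.3% | 1.7 |
| 5% | assumption | 16.2 | 80.8% | 4.3 |
| 10% | assumption | 32.4 | 76.5% | 8.5 |

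The choice of q matters little. At f = 0.60%, q = 60% gives 0.4 points and q = 90% gives 0.5. The last three rows lie above the interval from the cited data and have no source in the documents. They show only how the effect would grow if post-RFA patients failed more often.

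**Step 4: direction by measure.** For completion, excluding failures can only flatter the device. For preference and willingness it flatters the device if failures are less favourable than completers, which is likely. For mean IES the direction is not established: section 5.2.2 describes distress related to administration, and a subject who never swallowed the capsule had no sponge withdrawal to react to and might score low.

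**The case against.** The strongest reply is about size. On the documented rate the loss is about 2 subjects and half a percentage point. Section 1.3.1 puts the three known failures down to capsule size and ordinary pill-swallowing difficulty, not to a diseased esophagus. The failure count will also be on file, so the worst-case correction q × (1 − f) needs a reporting sentence and no new data. This stands for preference and willingness. It does not supply the failures' actual VAS, IES or preference answers, and section 6.2 does not commit to reporting the count.

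A reader might infer more than the documents support:

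- *That only those who tolerated the test are measured.* The filter is completion. A subject who completes with severe distress is still scored on every instrument.
- *That failures are replaced by subjects who can swallow the device.* Section 4.4 rules out replacement after a completed first administration and is silent on the rest. Silence is not a replacement rule.
- *That all four measures are biased towards the device.* This is not shown for mean IES (step 4).
- *That strictures will push the failure rate well above 0.6%.* Exclusion criterion 4 in section 4.2 covers only strictures that preclude passage, but section 1.3.1 lists any history of stricture as a reason for exclusion and says a recent endoscopy will have documented its absence. The two texts conflict, so neither alone supports a forecast of the failure rate.
- *That a failed attempt means an unwilling subject.* Section 5.1.3 itself provides for subjects who will try again after a failed swallow. Counting failures as unwilling is a worst case and belongs in a sensitivity analysis.

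**Conclusion.** The point holds as one of structure: as written, acceptability is estimated in completers only, and the plan does not report the proportion who could not complete. Confidence in this is high, because it follows directly from sections 4.4, 5, 5.1.3, 5.2 and 6.3 read together.

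The documented size is small: about 2 of 324 subjects and about 0.5 points on an 85% willingness figure, or about 6 subjects and 1.5 points at the upper confidence limit. This assumes that the UK primary-care rate carries over, that q is 85%, and that every failure is unwilling. No rate is given for post-RFA patients, so a larger effect cannot be excluded, but it cannot be claimed either. The plan should be changed because the remedy is cheap and would let the trial show that the loss is small.

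**What to change.** 1. **Sections 4.4, 5 (note 2) and 5.1.3.** State that subjects who attempted but did not complete the Cytosponge stay in the study for data collection: VAS before the endoscopy, and the IES and preference/willingness questionnaire at day 7. The rule on device attempts is not touched.
2. **Section 6.3.** Define two populations. For acceptability: all consented subjects who attempted the Cytosponge, whether or not pathology is available. This also keeps completers without pathology results, whom the present definition drops although acceptability does not need pathology. For accuracy: completers with pathology, as now.
3. **Section 6.2.** Report the swallowing/completion failure proportion with a 95% CI as an acceptability result. Add a sensitivity analysis counting failures with missing questionnaires as not willing or not preferring the device.
4. **Consistency.** Reconcile sections 1.3.1 and 4.2 on stricture history, and reconcile the rank of acceptability between sections 2 and 6.2 and sections 3.1, 3.3 and 3.4.

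The cost is protocol wording, a few extra phone calls, and probably slightly less favourable acceptability figures.

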## 5 Study Procedures

Assessment	Screening/Enrollment Visit	Follow-Up Phone Call (7 days +/- 2 days after Enrollment)	Repeat Cytosponge (30 days +/- 10 days after Enrollment)
Informed Consent Form	X		
Demographics	X		
Medical History	X		
Inclusion/Exclusion Criteria	X		
Cytosponge Administration	X		X 
Visual Analogue Scale	X 		
Routine Care Endoscopy with Biopsy	X 		
Impact of Events Scale		X	
Procedure Preference and Acceptability Questionnaire		X	
Adverse Events	X	X	X

If the initial Cytosponge sample is inadequate, sites will be notified and subjects will be asked to return for repeat Cytosponge administration 30 days (+/- 10 days) after the initial Cytosponge administration. Only the Cytosponge administration will be repeated. Questionnaires and the endoscopy procedure will not be repeated on these patients.

VAS should be administered immediately following completion of the Cytosponge and prior to the upper endoscopy.

Routine care biopsies should be taken during the endoscopy following the Cytosponge as this is considered standard of care for the target population. No research-specific biopsies will be obtained during the procedure.

Only those events that are potentially related to participation in this research study must be reported. See section 7.2 for definition of a reportable adverse event.

### 5.1 Screening/Enrollment

During screening/enrollment, eligibility is assessed and those eligible and interested in participating are consented on the study. Once consent is obtained, subjects will undergo administration of the Cytosponge, complete a questionnaire and proceed with routine care upper endoscopy immediately following completion of the Cytosponge in which biopsies are taken for clinical purposes and sent to pathology.

#### 5.1.1 Assessments

The following will be completed during the screening/enrollment visit:

- Eligibility review
- Informed consent
- Cytosponge administration
- Visual Analogue Scale
- Routine care upper endoscopy with biopsy
- Adverse event assessment
- Enrollment Case Report Form (eCRF): This captures demographics including race, ethnicity, gender, and year of birth, relevant BE medical history including documentation of endoscopic procedures received to date as well as pathology findings and endoscopic

history related to current diagnosis. This will also capture the date the Cytosponge was sent to the [name] Lab for analysis

### **5.1.2 Consenting Procedure**

If a subject is screened eligible and interested in the study, the subject will be consented on the study prior to any study procedure. Written informed consent will be obtained by qualified study personnel. Documentation of the consent process will be maintained in the subject's research record.

Subjects will be given ample time to review the consent document and ask any questions they may have. A copy of the written consent form will be provided to the subject and the original maintained in the subject's research record.

If subjects meet all inclusion and none of the exclusion criteria and consent to the study, they will be enrolled in the study. Subjects will be assigned a unique subject code. Each institution will be provided a list of subject codes to use.

### **5.1.3 Cytosponge Administration**

The Cytosponge™ device (referred to hereafter as the "Cytosponge") will be supplied by Covidien GI Solutions to the participating sites. Study sites will be responsible for storage and accountability of the device. The Cytosponge lifetime/use by date will be confirmed on the product packaging. The device received FDA 510(k) clearance on November 26, 2014 (K142695). The Cytosponge device consists of a spherical 3.0 cm diameter reticulated polyester foam compressed and encapsulated in a standard vegetarian capsule (size 00).

Subjects will undergo administration of the Cytosponge™ according to the IFU. Briefly, subjects will be placed in the seated position and will swallow the capsule with 150 – 250 mL of water. Additional water may be used if necessary. The sponge is attached to a length of suture material which passes out through the capsule. The suture is affixed to a retainer card which is held by the subject or administrator to prevent inadvertent swallowing of the suture. The string is to be held without tension as peristalsis and gravity advance the capsule into the stomach.

The capsule dissolves in the stomach, allowing the sponge to expand to its full size. Seven minutes and 30 seconds to ten minutes after ingestion, the sponge is then withdrawn by gentle traction on the suture, collecting cells from the lining of the esophagus in passing.

After retrieval, the string is cut and the retrieved foam sphere containing the cytological specimen is immersed in fixative and stored refrigerated (1° to 12°C [34° to 54°F]) until shipped. Samples will be shipped in batches to the [name] Lab in Cambridge. On arrival at the [name] lab, the fixative is spun in a centrifuge, and the pelleted cells are embedded in paraffin using standard techniques. The blocks are sectioned and stained for trefoil factor 3, where any staining is considered positive for the assay.

If a subject fails to swallow the Cytosponge, the subject will be asked to swallow again. Subjects who are willing to try again will be asked to wait 5 minutes before the Cytosponge is presented to them again. Subjects will be able to try up to three times before they are classified as "Cytosponge swallowing failure" and discontinued by the investigator.

### **5.1.4 Routine Care Endoscopy with Biopsy**

After Cytosponge administration is complete, subjects will undergo routine care upper endoscopy, with assessment of BE (where applicable), and biopsy per accepted surveillance or screening recommendations. Routine care tissue biopsies will undergo standard processing and H&E staining at the home institution, with assessment by expert gastrointestinal pathologists.

### **5.1.5 Adverse Event Assessment**

Subjects should be assessed for any adverse events that occur before, during, or after Cytosponge administration. Only those events that are potentially related to participation in this research study must be reported to the lead site. See section 7.2 for the definition of a reportable adverse event. Sites are responsible for following local IRB/EC guidelines for reporting adverse events to their local IRB/EC.

## **5.2 Follow-Up Phone Call**

Subjects will be contacted 7 days (+/- 2 days) following the Cytosponge and upper endoscopy procedures. During this phone call, adverse events will be assessed and subjects will complete questionnaires. Participation in the study is complete when subjects have completed the follow-up phone call.

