There are no plans for repeat testing or duplicate enrollment. Enrolled subjects will be administered the cytosponge one time, on the date of an endoscopy scheduled for routine care, prior to the endoscopy. Subjects can only participate one time. The only exception is for subjects who have an inadequate sample on the initial Cytosponge. These subjects will be asked to return for repeat Cytosponge administration 30 days (+/- 10 days) after the initial administration.

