## **5.3 Repeat Cytosponge Administration**

If the initial Cytosponge sample is inadequate, sites will be notified and subjects will be asked to return for repeat Cytosponge administration 30 days (+/- 10 days) after the initial Cytosponge administration. Only the Cytosponge administration will be repeated. Questionnaires and the endoscopy procedure will not be repeated on these patients. See section 5.1.3 for details on the Cytosponge administration procedure. The Repeat Administration eCRF should be completed.

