### **Adverse Event Reporting Period**

The study period during which adverse events must be reported is normally defined as the period from the initiation of any study procedures to the end of the study treatment follow-up. For this study, the study treatment follow-up is defined as 30 days following completion of the biomarker panel.

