### **Post-study Adverse Event**

All unresolved adverse events should be followed by the investigator until the events are resolved, the subject is lost to follow-up, or the adverse event is otherwise explained. At the last scheduled visit, the investigator should instruct each subject to report any subsequent event(s) that the subject, or the subject's personal physician, believes might reasonably be related to participation in this study. The investigator should notify the study sponsor of any death or adverse event occurring at any time after a subject has discontinued or terminated study participation that may reasonably be related to this study. The sponsor should also be notified if the investigator should become aware of the development of cancer or of a congenital anomaly in a subsequently conceived offspring of a subject that has participated in this study.

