### **7.2.2 Recording of Adverse Events**

At each contact with the subject, the investigator must seek information on adverse events by specific questioning and, as appropriate, by examination. Information on all adverse events should be recorded immediately in the source document, and also in the appropriate adverse event module of the electronic case report form (eCRF). All clearly related signs, symptoms, and abnormal diagnostic procedures results should be recorded in the source document, though should be grouped under one diagnosis.

All adverse events occurring during the study period must be recorded. The clinical course of each event should be followed until resolution, stabilization, or until it has been determined that the study treatment or

participation is not the cause. Serious adverse events possibly related to the study that are still ongoing at the end of the study period must be followed up to determine the final outcome. Any serious adverse event that occurs after the study period and is considered to be possibly related to the study procedures or study participation should be recorded and reported immediately.

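### Section 7.1 ends the adverse event period 30 days after a biomarker panel that this study does not include, and a repeat Cytosponge is followed by no scheduled contact and no endoscopy

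*Combined protocol and SAP*

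**What the plan says.** **End of participation.** Section 5.2 says "Participation in the study is complete when subjects have completed the follow-up phone call", and section 4.4 gives the same rule. The call is made 7 days (+/- 2) after the sponge and endoscopy.

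**End of the adverse event period.** Section 7.1 (Adverse Event Reporting Period) runs it from the first study procedure to the end of study treatment follow-up, and then says "the study treatment follow-up is defined as 30 days following completion of the biomarker panel". Section 7.2.2 attaches a duty to that period: "All adverse events occurring during the study period must be recorded". Section 7.2 limits what must be reported to study-related events.

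**Second exposure.** Section 3.1 restricts each subject to one administration, and adds: "The only exception is for subjects who have an inadequate sample on the initial Cytosponge". Sections 3.1, 5 and 5.3 place the repeat 30 days (+/- 10) after the first. The section 5 table gives the repeat its own column, with the adverse event row marked. It is the last column. Section 5.3 adds: "Questionnaires and the endoscopy procedure will not be repeated on these patients".

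**Handling of device problems.** Section 1.3.1 has every administered sponge inspected for fracture or incomplete retrieval. A detached sponge is to be retrieved, and bleeding investigated and treated, at the routine endoscopy that follows administration.

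**Late events.** Section 7.1 (Post-study Adverse Event) has the investigator tell subjects at the last scheduled visit to report later events, and notify the sponsor of any possibly related event at any time after participation ends. Section 7.2.2 requires possibly related late serious events to be recorded and reported immediately.

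**The concern.** A recording period needs an end date that sites can apply. This one is tied to an item that is not in the schedule of assessments, the procedures or the case report form table. The nearest candidate is trefoil factor 3 staining. It is a single stain on sponges shipped in batches to an outside laboratory, and no completion date is set for it. Two sites, or two coordinators, could stop recording at different times and both believe that they were following the protocol.

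The repeat sponge raises a second, related issue. The protocol's closing rules were written for a subject with one sponge, one endoscopy and one call. A subject with an inadequate sample swallows the device again after the point at which the protocol calls participation complete. That subject has no later contact, and does not have the endoscopy that the risk section presents as the remedy for detachment or bleeding. At stake are the completeness of active safety follow-up after the second exposure and a workable plan if the device fails at that visit.

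**Working it through.** The plan gives no figure to reproduce. The check is arithmetic on visit windows, with day 0 as the first Cytosponge, and a comparison of sections.

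**Inputs**
- Follow-up call: 7 +/- 2, so days 5 to 9 (section 5.2).
- Repeat Cytosponge: 30 +/- 10, so days 20 to 40 (sections 3.1, 5 and 5.3).
- Adverse event checks: the marked cells of the section 5 table.
- Sponge detachment: under 1% of administrations (section 1.3.1).

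**1. Does the repeat always fall after the call?**
- Shortest gap: 20 - 9 = 11 days.
- Nominal gap: 30 - 7 = 23 days.
- Longest gap: 40 - 5 = 35 days.

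The windows do not overlap, so every repeat comes after the stated end of participation.

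**2. When does the adverse event period end?** The anchor is undefined, so each line below is an assumed reading.
- Anchor is the first sponge: 0 + 30 = day 30. This covers 30 - 20 = 10 days after a day-20 repeat and 30 - 30 = 0 days after a day-30 repeat. It ends 40 - 30 = 10 days before a day-40 repeat.
- Anchor is the repeat sponge: 20 + 30 = day 50 to 40 + 30 = day 70.
- Anchor is completion of the trefoil factor 3 stain: no date can be computed.

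For a repeat subject, the two computable readings alone put the end anywhere from day 30 to day 70. Both differ from the day 5 to 9 call.

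**3. Scheduled adverse event checks**
- First exposure: enrollment visit + call = 2, plus a same-day endoscopy.
- Second exposure: repeat visit = 1, with no endoscopy.
- After the repeat visit: 0.

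**4. Rescue plan.** Section 1.3.1 says that the endoscopy routinely and immediately follows sponge administration. Section 5.3 says that it is not repeated. The two statements cannot both hold for a repeat, and section 5.3 offers no substitute.

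**5. Effect of adding a call 7 +/- 2 days after the repeat**
- Earliest: 20 + 5 = day 25.
- Nominal: 30 + 7 = day 37.
- Latest: 40 + 9 = day 49.

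**The case against.** The strongest reply is that little depends on the end date. Only study-related events are reportable, and related events stay reportable at any time under the post-study rule in 7.1 and, if serious, under 7.2.2. An adverse event window may also properly outlast the last visit. All of this stands. It rules out the inference that events after a repeat would go unreported under the protocol. What remains is the recording duty in 7.2.2, which covers all adverse events and has no usable end.

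A second reply is that the repeat is plainly part of the study, with its own table column, adverse event check and case report form. That also stands. The 11 to 35 days therefore measure a conflict in the drafting and should not be read as a stretch of lost safety data.

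A reader might further infer that the self-report instruction is given before the second exposure, because section 4.4 names the call as the last visit. The documents do not support this. For a repeat subject the last scheduled visit is naturally the repeat visit, and the instruction covers any later event in any case.

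A reader might also infer that a detached sponge could go unnoticed. It should not, because section 1.3.1 has every sponge inspected. What is missing is the means of retrieval.

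Finally, the counts of 2 and 1 checks compare unlike exposures: the first call follows a sponge plus endoscopy with biopsies, and the listed risks are mainly acute. This is fair, and it makes the extra call an inexpensive improvement rather than the correction of an error. The protocol does ask for blood thinners to be withheld for 7 days after the procedures, so a day-7 check fits its own view of the risk period, although that rule covers endoscopy and sponge together.

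**Conclusion.** The end of the adverse event period in section 7.1 is wrong as written: it refers to a procedure that is not part of this study, so sites cannot apply it. For repeat subjects, sections 4.4 and 5.2 close participation before the second device exposure, no contact follows that exposure, and the rescue described in 1.3.1 is not available. The follow-up call and the booking rule proposed for these subjects are cheap improvements.

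Severity is minor. The issue touches active safety ascertainment and the contingency plan only, in a subgroup whose size the documents do not state and for which no estimate is made here. Detachment is put at under 1% of administrations. Nothing here bears on sensitivity, specificity or the acceptability results.

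The conclusion assumes that no biomarker panel is defined in the flow diagrams of sections 3.1 and 3.2, which could not be read. No such panel appears in the text, the schedule or the form table.

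**What to change.** 1. **Section 7.1.** Replace the whole definition of study treatment follow-up, including the 30 days, so that it ends with *the follow-up call 7 days (+/- 2) after the most recent Cytosponge administration*. Changing only the anchor would leave a 30-day recording duty beside active collection that stops at a day 5 to 9 call. State that later related events fall under the post-study rule in 7.1 and the late serious event rule in 7.2.2.
2. **Sections 4.4, 5.2 and 5.3.** State that participation for repeat subjects continues through the repeat visit and one brief call 7 days (+/- 2) later, for adverse events only and without questionnaires. Add the call to the section 5 table.
3. **Section 5.3.** Require the repeat to be booked at a time when same-day endoscopy can be arranged if the sponge detaches or bleeding is seen.

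**Cost.** Wording in four sections and one table entry, one short call per repeat subject, and fewer slots to choose from for repeats. An extra endoscopy is needed only if the sponge detaches or bleeding occurs. Unrelated events after the final call would no longer be recorded, but section 7.2 does not make those reportable now.
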